15.2 Safety evaluation

15.2.1 Calculation or derivation of safety variables

All adverse events will be analysed at AstraZeneca R&D Lund, Sweden, by means of descriptive statistics and qualitative analysis. AEs will be listed for each subject and summarised by body system and preferred term assigned to event by using MedDRA. Adverse events will also by summarised by intensity and causality to study drug/study procedures (as judged by the investigator).

Safety laboratory data, vital signs and ECG data will be listed for each subject and summarised by treatment groups. These data will be presented using descriptive statistics for each visit and assessment time within the framework of the standard laboratory safety evaluation at AstraZeneca R&D Lund, Sweden. For clinical chemistry and haematology, the minimum ways to present the results are: mean values over time, individual values over time, shift tables, and when appropriate also shift plots, and presentation of individual clinically important abnormalities at any time during treatment (ie, outside the defined extended reference ranges). AstraZeneca extended reference ranges should be used for the identification of individual clinically important abnormalities (treatment emergent laboratory changes, TELCs). For urinalysis the minimum way to present data are shift tables presenting the number of patients with categorical changes from baseline versus on-treatment values. Vital signs data (ie, body temperature, pulse, systolic blood pressure, and diastolic blood pressure) are to be presented in the same way as for clinical laboratory data. The minimum ways to present numeric ECG variables (ie, heart rate, QTc intervals) are the same as for the clinical laboratory data. In addition, shift plots and additional graphical presentations can be included.

All safety data will be compared between the treatments at each dose level and placebo.

An AstraZeneca expert will review all laboratory results and data for vital signs outside the AstraZeneca extended reference limits, during the safety evaluation and Other Significant AEs (OAEs) will then be identified, as described in Section 4.6.1.1, Definitions. Follow-up information about such findings may be requested.

15.3 Statistical methods and determination of sample size

15.3.1 Statistical evaluation

The statistical analyses will be performed by AstraZeneca R&D Lund, Sweden. Safety data will primarily be comprehensively described in terms of figures, descriptive statistics and listings, in order to facilitate safety and tolerability assessments of different doses and the pharmacokinetic properties of the drug. The evaluation of pharmacodynamic data will be focused on dose-response patterns of the drug.

15.3.2 Description of variables in relation to hypotheses

 FEV_1 and potassium will be the primary variables of local and systemic effects. $FEV_1 E_{max}$ will be the primary variable to determine the bronchodilatory potency of the drug. FEV_1 E_{22-26} will be the primary measure of the duration of the bronchodilatory effect. Potassium E_{min} will be the primary measure of the potency regarding systemically mediated side effects.

15.3.3 Description of analysis sets

The full analysis set will consist of all patients with data collected from at least 2 study periods (placebo plus 1 period with active drug). The safety data set will consist of all patients with data from at least 1 study day.

15.3.4 Methods of statistical analyses

Pairwise comparisons for pharmacodynamic parameters (between active drug and placebo, and between different doses of active drug) will be made using analysis of variance models. Depending on the outcome at the dose levels, separate models within each cohort or a combined model will be chosen. For dose-response, if appropriate, an Emax model will be fitted to data using a mixed effects model.

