6.3.4 Methods of statistical analyses

All data will be graphically illustrated and presented by descriptive statistics for each treatment group. Safety and pharmacodynamic data will be compared between active treatment and placebo at each dose level. Placebo subjects from different dose-levels will be pooled for the comparisons. For pharmacodynamic parameters comparisons will be made using analysis of variance model with fixed factor treatment and using baseline as a covariate. Dose-response is considered an exploratory part of the evaluation, and the final model will be data driven. AEs will be analysed by means of descriptive statistics and qualitative analyses.

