Part B of the study comprises 6 visits (see Figure 2 and Table 6); 2 screening visits, 1 placebo visit, 2 treatment visits and a follow-up visit.

Visits 1 and 2 are screening visits. At Visit 1 informed consent will be obtained before any study related procedures are undertaken. At Visit 2, a stepwise reversibility test to check eligibility will be done. Visits 1 and 2 will be performed within 30 days prior to Visit 3.

Visits 3-5 are the treatment visits when the patients will receive placebo and single doses of AZD3199 inhaled via nebuliser. Study measurements will be taken pre-dose and repeatedly after administration of study drug up to 48 hours as scheduled in Table 7. However, time points for measurements may be adjusted if felt necessary. Visit 3 should be performed at least 72 h after Visit 2.

Visit 6, the follow-up visit, will be performed within 10 ± 3 days after last administration of study drug. The length of the follow up period may be adjusted if felt necessary. On this visit also reversibility after 9 µg formoterol will be tested.

Figure 2 Part B - Study design

Visit 1 Subject Information	Visit 2 Medical examination, stepwise reversibility	Visit 3 Placebo	Visit 4 AZD3199 (low)	Visit 5 AZD3199 (high)	Visit 6 Follow-up, reversibility test (formoterol)
_ ,	etween Visit 1 and 3 between Visit 2 and 3				10 ± 3 days after last dose

Table 6Part B - Study plan

Event	Visit 1	Visit 2	Visit 3	Visit 4	Visit 5	Visit 6
	Screen- ing 1	Screen- ing 2	Placebo	AZD3199 low dose	AZD3199 high dose	Fol- low-up
Informed consent/Allocation of enrolment code	Х					
Demographics	Х					
Height and weight	Х					
Medical/surgical history		X				

60(95)

Approved

Approved by

(Continued)

Table 6	Pa
Table 6	Pa

art B - Study plan

Event	Visit 1	Visit 2	Visit 3	Visit 4	Visit 5	Visit 6
	Screen- ing 1	Screen- ing 2	Placebo	AZD3199 low dose	AZD3199 high dose	Fol- low-up
Inclusion/exclusion criteria	Х	Х	X			
Physical examination		Х				Х
Spirometry ^a		Х	X	Х	Х	Х
Reversibility test with formoterol						Х
Stepwise Reversibility Test		Xb				
Concomitant medication		Х	Х	Х	Х	Х
Laboratory safety assessments	Х		X	Х	Х	Х
HIV and hepatitis B and C tests	Х					
Drugs of abuse test ^c	Х		X			
Alcohol breath test ^e		X	X			
Blood pressure, pulse		Х	X	Х	Х	Х
12-lead ECG		Х	Х	Х	Х	Х
Inhalation training		X	X	Х	Х	
Allocation of randomisation code			X			
Blood sampling for PGx			Xd			
Administration of study drug			X	Х	Х	
Telemetry monitoring (48 h)			X	Х	Х	
Blood sampling for PK				Х	Х	

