12.2 Rationale and risk/benefit assessment

12.2.1 Rationale for study design, doses and control groups

Part B of this study is designed to assess the efficacy, safety, tolerability and pharmacokinetic profile of inhaled AZD3199 when administered to patients with asthma in single doses. The study will help the selection of appropriate doses of AZD3199 for future studies.

Following a placebo administration, 2 single doses of AZD3199, 1 low and 1 high dose will be administered to two sub-groups of asthmatic patients in order to assess a graded dose bronchodilatation response. The non-randomised design with the fixed order of doses was chosen in order to allow for the dose given in Part B to be covered by an equal or higher dose in Part A. This design would automatically unblind the study site personnel, and therefore a single-blind study was selected in order to avoid bias from the patients' knowledge of treatment. Placebo administration was chosen to obtain reference data and to avoid bias. Food/water intake will be standardised/restricted to keep the conditions similar between patients and visits and to minimise variability on the ECG monitoring and potassium levels.

 β_2 -agonists are functional antagonists. Stimulation of β_2 -adrenoceptors, located in the cell membrane of smooth muscles in the airways, decreases tone, irrespective of the cause of the constriction, ie, the calibre of constricted airways is increased. Forced expiratory volume during in the first second (FEV₁) is used as the bronchodilatation effect variable. Asthmatic patients with a known step wise reversibility (increase in FEV₁ upon administration of a β_2 -agonist) will be included to be able to assess dose-response. The study is restricted to men, since sufficient reproduction toxicology data in female animals are not yet available. The inclusion and exclusion criteria for Part B are chosen in order to select patients who are known to be free from any significant illness other than asthma.

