15.1 Pharmacokinetic / pharmacodynamic evaluation

15.1.1 Calculation or derivation of pharmacokinetic variables

The pharmacokinetic analyses will be performed by the Department of Clinical Information Science, AstraZeneca R&D Lund, Sweden.

From the plasma concentrations of AZD3199 collected following a single dose, pharmacokinetic parameters will be calculated using standard non-parametrical methods. The pharmacokinetic parameters will include: the maximum plasma drug concentration (C_{max}) , the time to maximum plasma drug concentration (t_{max}) , the area under the (plasma drug concentration-time) curve from time zero to infinity (AUC), terminal half-life of drug in plasma ($t_{1/2}$), apparent plasma clearance (CL/F).

15.1.2 **Calculation or derivation of pharmacodynamic variables**

Pharmacodynamic variables in this study will include potassium and lactate concentrations, blood pressure, heart rate, QTcB, tremor, palpitations and FEV₁. For each variable the maximum effect during the post-dose measurement interval (the minimum value, Emin, for

Approved by

potassium and diastolic blood pressure, and the maximum value, E_{max} , for other variables) and the average effect, E_{av} (AUC/length of interval), will be computed and used as variables of systemic and local effects. In addition, for FEV₁, the effect during 22 - 26 hours post-dose, E_{22-26} , will be calculated. Further, data collected at each assessment time will be used in the statistical evaluation to follow the duration of effect of the drug.

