15.3.5 Determination of sample size

This is an initial study to evaluate the efficacy of AZD3199 in patients with asthma. The study will be performed under SAD-like conditions, and the number if patients has therefore been set with respect to the possibility to conduct the study, rather than to be able to detect a certain level of effect. From previous experience with formoterol, a within-subject coefficient of variation of 4% in FEV₁ could be expected. With 8 patients, and a 2-sided test at the 5% significance level, there will be an 80% power to detect a true pairwise difference (within cohort) of 7%. To allow for more than 2 doses of AZD3199 being tested, 2 cohorts of 8 patients each will be used, all starting with placebo, and then given 2 doses each of AZD3199 in ascending order.

90(95)

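### Part B's analysis section makes no provision for each visit's pre-dose value, although Part A's does and the fixed dose order lets a visit-to-visit shift pass into the dose-placebo difference

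*Protocol*

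**What the plan says.** **Part B model.** Protocol section 15.3.4 says that pairwise comparisons of pharmacodynamic parameters with placebo and "between different doses of active drug) will be made using analysis of variance models". Separate models per cohort or one combined model may be chosen later. No factor and no covariate is named.

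**Part A model.** Section 6.3.4 is more specific: "comparisons will be made using analysis of variance model with fixed factor treatment and using baseline as a covariate".

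**Part B variables.** Section 15.1.2 takes the post-dose minimum for "potassium and diastolic blood pressure, and the maximum value, E_{max} , for other variables", and adds, for FEV1, "the effect during 22 - 26 hours post-dose". None of these is defined as a change from, or ratio to, the pre-dose value. Section 15.3.2 states that FEV1 E_max "will be the primary variable to determine the bronchodilatory potency of the drug", and makes FEV1 E22-26 and potassium E_min the primary measures of duration and of systemic effect.

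**Data and order.** Section 12.1 says of Visits 3 to 5: "Study measurements will be taken pre-dose and repeatedly after administration of study drug up to 48 hours". Table 7 has a pre-dose column for both FEV1 and potassium. Figure 2 gives the order as placebo, low dose, high dose, and section 12.2.1 explains it: "The non-randomised design with the fixed order of doses was chosen" so that each Part B dose is covered by an equal or higher dose in Part A.

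**The concern.** A baseline covariate is written into the part of the study that has concurrent randomised placebo, and not into the part that lacks it. In Part B nothing in the design cancels a change in level between Visit 3 and Visits 4 or 5. Order is the same for everyone, so a visit effect cannot be estimated separately from treatment. The value measured just before dosing at the same visit is the planned measurement that can show such a change and partly correct for it. As written, neither the definition of the variables nor the model uses it.

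At stake are the primary Part B comparisons. If patients arrive at an active visit with better or worse airway calibre than at the placebo visit, and the difference lasts through the day, the dose-placebo estimate is raised or lowered by that amount. The same reasoning applies to potassium.

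**Working it through.** **Inputs from section 15.3.5:** 8 patients per cohort, two-sided 5% test, "a within-subject coefficient of variation of 4"% in FEV1, and 80% power for a 7% pairwise difference.

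**Inputs assumed:** the size of a shift shared by all patients between visits, and the share of the 4% within-patient variance that is day level (common to pre-dose and post-dose values at a visit). The protocol gives neither.

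**Step 1: the plan's own figure.** The SD of a paired difference is √2 × 4% = 5.66%. A paired t-test (7 df) at a 7% difference has 77.8% power with 7 patients and 85.0% with 8. So 8 is the smallest number reaching 80%, and the difference detectable with 80% power is 6.5% (6.8% on the log scale), which rounds to 7%. The stated figure reproduces.

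**Step 2: a shift without any pre-dose term.** Take the model with patient and treatment as factors over three visits: 24 observations − 8 patients − 2 treatment contrasts = 14 residual df.
- Standard error of a dose-placebo contrast: 4% × √(2/8) = 2.0%.
- With no drug effect, the expected estimate equals the shift, so the noncentrality is shift ÷ 2.0%.
- The critical t with 14 df is 2.145.

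| Assumed shift | Noncentrality | Rejection rate |
|---|---|---|
| 1% | 0.50 | 7.5% |
| 1.5% | 0.75 | 10.8% |
| 2% | 1.00 | 15.4% |
| 3% | 1.50 | 28.7% |

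The false-positive rate is at least twice nominal from a shift of about 1.5%.

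**Step 3: the same visit's pre-dose value added (13 df).** In simulation, outcome = day level + noise + drug effect and pre-dose = day level + independent noise, with total within-patient SD 4% in each. The within-patient slope on pre-dose is then about equal to the day-level share, so the bias left is about shift × (1 − share). For a 3% shift that is 2.1, 1.5, 0.9 and 0.45 percentage points at shares of 30%, 50%, 70% and 85%.

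| Day-level share | False positives, 3% shift | False positives, 2% shift | Power for a true 5% effect, no shift |
|---|---|---|---|
| No pre-dose term | about 29% | about 15% | about 64% |
| 30% | about 15% | about 10% | about 65% |
| 50% | about 11% | about 8% | about 73% |
| 70% | about 8% | about 7% | about 88% |
| 85% | about 6% | about 6% | about 98% |

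At a share of zero the covariate costs 3 to 4 points of power (about 64% to 60%) and removes no bias.

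**Step 4: change from pre-dose as an alternative.** This removes a persistent shift entirely, but its precision depends more heavily on the correlation. The simulated SD of the dose-placebo estimate, unadjusted against change from pre-dose, is 1.92 against 2.76 at correlation 0, 1.94 against 1.93 at 0.5, and 1.97 against 1.22 at 0.8. With the covariate the SDs are 1.99, 1.73 and 1.20. The covariate is the safer choice when the correlation is unknown.

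**The case against.** **Silence is not exclusion.** A reader might infer that Part B has decided against baseline adjustment. The text does not support that. Section 15.3.4 lists no terms at all, not even patient, and section 6.3.4 calls a model with a covariate an analysis of variance, so the phrase does not rule one out. An analysis plan that is not shown could add it. This stands, and the point is limited to what section 15.3.4 fails to provide for. What remains is that one protocol names the covariate for Part A and not for Part B, and an analysis-plan author could fairly take the contrast as meant.

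**The bias comes from the fixed order.** This also stands. The order is disclosed and justified, the missing covariate does not create a shift, and adding it does not remove one completely.

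**A gain in precision is not assured.** A reader might infer that precision is necessarily lost without the covariate. That depends on a within-patient correlation the protocol does not give. Nor does section 15.3.5 say whether the 4% is already baseline-adjusted; if it is, the gain in step 3 is overstated.

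**Visit conditions are controlled.** Stable background medication, withholding periods, standardised meals, morning dosing and at least one week between active doses all limit shifts. They make a large shift less likely but do not exclude one, and no pre-dose FEV1 stability requirement is stated for Visits 3 to 5.

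**The study is exploratory.** Part B's size was set by feasibility, so nominal error rates carry less weight. That lowers the stakes, but FEV1 E_max and E22-26 still carry the primary objective.

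**Conclusion.** The point holds as a gap in specification with a cheap remedy. Section 15.3.4 does not provide for the pre-dose value, the primary variables do not use it, and with a fixed order a persistent shift between visits passes one-for-one into the dose-placebo difference. For FEV1, with 8 patients and a 4% within-patient CV, shifts of 1.5% to 3% would raise the false-positive rate to about 11% to 29%.

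These rates rest on assumed shifts; the protocol neither states nor implies that one will occur. The improvement from adjustment rests on an assumed day-level share: at a 3% shift, false positives fall to about 15% if the share is 30% and about 6% if it is 85%. Changes that arise after dosing remain confounded with dose whatever covariate is used. E22-26 is measured the next day, where the link to that visit's pre-dose value is less certain. Potassium was not simulated, so the figures should not be carried over to E_min.

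**What to change.** In section 15.3.4, state that the Part B pairwise comparisons use analysis of covariance with patient and treatment as factors and the same visit's pre-dose value of the variable as covariate. Apply this to FEV1 E_max, E_av, E22-26 and the by-time-point values, and to potassium E_min and E_av, and carry it into any combined-cohort model. Tabulate mean pre-dose FEV1 and potassium by visit beside the treatment estimates, so that a shift is visible. State that visit and dose are confounded and that the covariate removes only the part of a shift reflected in the pre-dose value.

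The cost is a change of wording and one residual degree of freedom (14 to 13 within a cohort). No new measurement, visit or patient is needed. If pre-dose values prove uninformative, about 3 to 4 points of power are lost.

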15.3.5 Determination of sample size

This is an initial study to evaluate the efficacy of AZD3199 in patients with asthma. The study will be performed under SAD-like conditions, and the number if patients has therefore been set with respect to the possibility to conduct the study, rather than to be able to detect a certain level of effect. From previous experience with formoterol, a within-subject coefficient of variation of 4% in FEV₁ could be expected. With 8 patients, and a 2-sided test at the 5% significance level, there will be an 80% power to detect a true pairwise difference (within cohort) of 7%. To allow for more than 2 doses of AZD3199 being tested, 2 cohorts of 8 patients each will be used, all starting with placebo, and then given 2 doses each of AZD3199 in ascending order.

90(95)

15.4 Interim analyses

No formal interim analysis will be performed. However, prior to each dose escalation, data from the preceding dose level(s) will be reviewed in order to decide what the next appropriate dose would be.

15.5 Data presentation

Safety data will be described as listings, individual graphs and statistical descriptive summaries by dose level of AZD3199.

15.6 Safety Review committee

Safety and tolerability will be evaluated by a Safety Review Committee (SRC).

The SRC will consist of medical expertise. The chairman of the committee will be the Clinical Study Team Physician. The other experts will be the Principal Investigator, the Medical Science Director and the Global Drug Safety Physician. Other relevant expertise (eg, medical, statistic, pharmacokinetic, drug safety) will be consulted if deemed necessary. The members of the committee will review interim study data and decide upon the progression of dosing from 1 dose level of AZD3199 to the next. Safety and tolerability data (ECG parameters, blood pressure, pulse, body temperature, safety laboratory variables, and adverse events), from at least the first 12 hours after dose, efficacy data (lung function) up to 26 hours after dose and available PK results will be evaluated prior to progression to the next dose level. Data obtained after the stated time points must be reviewed by the Investigator and communicated with the SRC. The SRC will decide whether to:

- continue to next planned dose
- adjust the next dose level
- postpone the next dose level
- terminate the cohort or the study

The decision of the SRC will have to be taken in consensus. The decisions and decision-making will be noted by the chairman and a written recommendation will be provided to the study site and IPS, AstraZeneca R&D, prior to the next scheduled dose escalation. The SRC and/or the principal investigator will have the full authority to terminate the study at any time during the course of the study.

16. ETHICS

16.1 Ethics review

AstraZeneca will provide Ethics Committees and Principal Investigators with safety updates/reports according to local requirements.

The final study protocol, including the final version of the Informed Consent Form, must be approved or given a favourable opinion in writing by an Ethics Committees as appropriate. The investigator must submit written approval to AstraZeneca before he can enrol any subject into the study.

The Principal Investigator is responsible for informing the Ethics Committee of any amendment to the protocol in accordance with local requirements. In addition, the Ethics Committee must approve all advertising used to recruit patients for the study.

16.2 Ethical conduct of the study

The study will be performed in accordance with the ethical principles that have their origin in the Declaration of Helsinki and are consistent with Good Clinical Practice, applicable regulatory requirements and the AstraZeneca policy on Bioethics.

